### **3.4. Tolerability of investigative examinations**

No data exist on patient tolerability/acceptability of HIDA scintigraphy or Bilitec monitoring. Studies of other catheter-based investigations involving probes with half the diameter of a Bilitec probe, have reported a significant impact on patient comfort (22, 23). Radiation exposure during HIDA scintigraphy is approximately 3 mSv (equivalent to 30 chest X-rays). Please see attached radiation safety report for further information.

### **3.5. Impact of study results**

A significant barrier to increased uptake of the LSAGB is the potential for increased bile reflux post-operatively, an area with a paucity of objective studies. Our study will provide additional data on the safety of the procedure, both generally and specifically relating to bile reflux, impacting surgical decision making in bariatric surgery. We hope to provide clinicians with clear evidence from which they can make informed decisions about the safety of the LSAGB.

With current data showing favourable results, including improved efficacy and decreased risk of complications, increased utilisation of the technique will result in improved short-term and long-term patient outcomes. Awareness of the incidence of bile reflux post-operatively will allow clinicians to treat any reflux early, preventing or at least delaying potentially detrimental health outcomes. These interventions will translate into decreased health expenditure, providing net health and economic benefit.

# 4. Study Plan and Design

## 4.1. STUDY TYPE

Prospective Cohort Study

## 4.2. INCLUSION CRITERIA:

Patients undergoing obesity surgery at the Royal Adelaide Hospital, The Queen Elizabeth Hospital, Burnside War Memorial Hospital, Western Hospital, Calvary Wakefield Hospital, Flinders Private Hospital or Ashford Hospital who have:

- Obesity of >5 years duration
- BMI>40 or >35 plus comorbidities
- Documented attempts at previous weight loss
- Age 18-60
- Good commitment to achieving weight loss
- Suitability for bariatric surgery

## 4.3. EXCLUSION CRITERIA:

Patients who have:

- Previously undergone obesity surgery
- Previously undergone gastric surgery
- Previously undergone gallbladder surgery
- Large abdominal hernias
- Pregnancy or are breast feeding
- Psychiatric illness
- BMI>65

## 4.4. SAMPLE SIZE:

*A sample size of 72 (24 in each of the 3 study arms) is required to find a significant difference in percentages of patients with bile reflux following 3 different types of operations.*

This was determined using a *Fisher's Exact Conditional Test for Two Proportions*, assuming a power of 80% and  $\alpha=0.05$ . A difference of 45% between worst and best operation in terms of reflux was considered (5% vs 50%, which represents a 'best estimate' of bile reflux post-operatively due to lacking published data). Because there is clustering on surgeon in this data, an inflation factor (IF) was used to account for correlation within surgeon. Inflation

factor= $1 + (m-1)p$  where  $m$ =cluster size and  $p$ =intra-class correlation coefficient (ICC) (<https://www.newton.ac.uk/files/seminar/20110815152516051-152821.pdf>). So IF for 5 surgeons and ICC=0.05 is 1.2. An additional 10% was then added to account for loss to follow-up. N per group was then multiplied by 3 (3 operation groups) to give total sample size needed.

A further 24 participants, from 1 surgical arm of the main trial, who have previously undergone surgical gallbladder removal (an exclusion criterion for the main trial) will also be recruited. This subset will allow us to compare the impact of gallbladder removal on the rate and severity of bile reflux for 1 operation. This sub-group of patients will not be subjected to the entire study protocol outlined below. They will only undergo the HIDA scan and the symptom questionnaire, but not the endoscopy.

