# 5. Outcomes

## 5.1. PRIMARY OUTCOMES:

- Scintigraphic evaluation of presence and degree of gastro-oesophageal bile reflux
- Impedance-based characterisation of oesophageal acidity, composition, duration and extent of oesophageal reflux
- Determination of presence of bile acids in gastric pouch and oesophageal fluid aspirates
- Determination of bile-acid induced gastric and oesophageal histological tissue changes

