## 5.2. SECONDARY OUTCOMES:

- Biliary gastritis/oesophagitis/other markers of mucosal inflammation in the stomach and oesophagus
- Weight Loss/BMI
- Metabolic changes
- Quality of life
- Operative time
- Rate of conversion from laparoscopic to open operative technique
- Post-operative surgical complications such as, anastomotic leak, infection, cardio-respiratory events, kidney injury, venous thromboembolism, and so on.
- Length of hospital stay
- Patient tolerability of investigations (hepatobiliary scintigraphy, oesophageal reflux tests and endoscopy with aspiration and biopsy), with regard to personal comfort prior to, during, and after the investigation.

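### Four unranked primary outcomes are compared across three operations, but the sample size rests on one unnamed binary reflux outcome, for one best-versus-worst pair, at unadjusted alpha 0.05

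*Protocol*

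**What the plan says.** Protocol section 4.4 says that 72 patients, 24 per operation, "is required to find a significant difference in percentages of patients with bile reflux following 3 different types of operations". The method is a "Fisher's Exact Conditional Test for Two Proportions", "assuming a power of 80% and" alpha 0.05. The contrast is stated openly: "A difference of 45% between worst and best operation in terms of reflux was considered", with rates of "5% vs 50%, which represents a 'best estimate' of bile reflux post-operatively due to lacking published data". The per-group number is inflated for clustering ("So IF for 5 surgeons and ICC=0.05 is 1.2"), raised by 10% for loss to follow-up, and multiplied by three. No rate is given for the third operation, and the section does not say which measurement decides whether a patient has bile reflux.

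Section 5.1 lists four primary outcomes in no order:
- the scan outcome, "Scintigraphic evaluation of presence and degree of gastro-oesophageal bile reflux";
- an impedance outcome with several measures;
- bile acids in gastric pouch and oesophageal aspirates;
- gastric and oesophageal histological change.

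Section 5.2 lists as secondary "Biliary gastritis/oesophagitis/other markers of mucosal inflammation in the stomach and oesophagus". Section 9 analyses the primary outcomes across the three operations with generic parametric, non-parametric and proportion tests. It mentions post-hoc comparison only for non-normal data.

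**The concern.** A sample size calculation supports a claim about the outcome and contrast it was made for. Here that outcome is binary and unnamed, and the contrast is one pair of operations out of three. The protocol gives primary status to four outcomes, some of which can be scored in several ways, and says nothing about which one leads.

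Two things are at stake. First, a false positive on any one of the four could be reported as the study's primary finding, so the 5% error rate of a single test does not describe the study. Second, the 80% power attaches to one outcome and one pair. A non-significant result on another primary outcome, or on a comparison with the middle operation, could be read as evidence of no difference when the study was never sized to find one.

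**Working it through.** **Inputs.** From section 4.4: 5% v 50%, alpha 0.05, power 80%, inflation 1 + (5 − 1) × 0.05 = 1.2, 10% for loss, three arms. From section 5.1: four primary outcomes. Assumptions: two-sided tests (the sidedness is not stated); a middle-operation rate between 5% and 50% (none is given); independence between outcomes where stated. Fisher and three-group exact results come from full enumeration of the binomial outcomes.

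**1. The plan's own figure.** Two-sided Fisher power for 5% v 50% is 77.7% at n = 16 and 81.3% at n = 17, so 17 per arm is needed. 17 × 1.2 = 20.4, rounded up to 21. 21 × 1.1 = 23.1, rounded up to 24. 24 × 3 = 72. The figure reproduces as an unadjusted calculation for one pair.

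**2. Chance of at least one false primary claim.**
- Four independent tests at exactly 5%: 1 − 0.95⁴ = 18.5%.
- Three unadjusted pairwise Fisher tests on one binary outcome, 24 per arm, all operations truly equal: 0.91% at a common rate of 5%, 7.5% at 50%.
- The same over four independent binary outcomes: 1 − (1 − 0.0091)⁴ = 3.6%, up to 1 − (1 − 0.075)⁴ = 26.8%.
- One three-group exact test per outcome instead of pairs: about 5% to 16% over the same rates.

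These use the full 24 per arm with no loss or clustering.

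**3. Power for what the protocol covers.** Effective size per arm is 24 × 0.9 / 1.2 = 18.

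| Question, n = 18 per arm | Power |
|---|---|
| 5% v 50%, one pair, alpha 0.05 | 84.4% |
| 5% v 50%, Bonferroni over three pairs (0.05/3 = 0.0167) | 65.3% |
| Three-group exact test, middle rate 5% to 50% | 80.6% to 92.7% |
| Three-group test and extreme pair both significant | 79% to 83% |
| 5% v 27.5% (middle rate assumed) | 31% |
| 27.5% v 50% (middle rate assumed) | 20% |

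For the other three primary outcomes the protocol gives no expected values, so their power cannot be calculated.

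**4. Which outcome could be the one sized.** The HIDA scan can be read as present or absent, and section 7.3 plans it for all participants. Section 4.5.5 offers impedance testing at 6 months only to patients with troublesome symptoms and a worse symptom score, so it cannot compare whole cohorts. Aspirates and biopsies come from endoscopy, which is planned before and after surgery in the main cohort but omitted in the added gallbladder group.

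**The case against.** The strongest reply is that section 4.4 is correct on its own terms. It states that it compares worst with best, and it claims no power for each pair. Read as a promise to detect some difference among three operations on one binary outcome, it is borne out by the three-group power in the table. This stands. A reader might infer from the reference to three operations that every pair has 80% power, or that 72 is simply too few; the text supports neither.

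The second reply is that test order and multiplicity rules are commonly left to a statistical analysis plan, which may exist. This stands in part. The error rate is uncontrolled in this protocol, not necessarily in the study. But the list of primary outcomes, and the outcome and contrast behind the sample size, are fixed here. A later Bonferroni correction would also undercut the unadjusted alpha used in 4.4.

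The third reply concerns size. Crossing four outcomes with three pairs gives 1 − 0.95¹² = 46%, and a reader might quote that. It should not be used: the protocol does not plan twelve tests, Fisher's test runs below its nominal 5%, and outcomes measuring the same reflux process are probably correlated. At low event rates the error may not exceed 5% at all.

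Finally, a reader might say that identical biopsy data sit at both primary and secondary level. Overlap between histological change in 5.1 and inflammation markers in 5.2 is likely, since section 9 assesses inflammation on biopsies. But the 5.2 items could also be read at endoscopy, so identity is not shown.

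**Conclusion.** The point holds in a limited form. Four unranked primary outcomes across three operations are paired with a sample size for one unidentified binary outcome and one extreme pair, at unadjusted alpha. The chance of a false primary claim can exceed 5%. The ranges in step 2 assume independent outcomes, and the pairwise ones also assume binary outcomes and unadjusted tests, so they indicate scale and are not estimates of the true rate.

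The total of 72 is not in error, and the power statement is sound for one overall test of one binary outcome. What lacks support is any extension to the other three primary outcomes, to contrasts with the middle operation, or to adjusted pairwise tests. The 31% and 20% depend on an assumed middle rate of 27.5%. All power figures at n = 18 accept the protocol's inflation factor of 1.2, which is not examined here.

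**What to change.** 1. In section 5.1, name one primary outcome and state in 4.4 that it is the one sized. Bile reflux present or absent on the 6-month HIDA scan is the best supported choice. Section 4.4 does not dictate it: the primary objective speaks of bile acids in the stomach and oesophagus, and aspirates, unlike the scan, are also taken before surgery. The investigators must decide and say so.
2. Make the other three outcomes secondary, or rank them in a fixed testing order.
3. Test the lead outcome with an overall three-group exact test at 0.05, and proceed to pairwise tests at 0.05 only if it is significant. With three groups this is a closed procedure, so alpha need not be split.
4. In 4.4, state that the 80% power applies to this outcome and to a 5% v 50% difference only. Show any power for the middle operation over a range of assumed rates, labelled as assumptions.
5. Say how the inflammation outcomes in 5.2 differ from the histological outcome in 5.1.

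The cost is a protocol amendment with no added patients. Three outcomes lose primary status or take a lower rank, and power to declare the extreme pair different becomes 79% to 83% instead of 84%, so it can fall just below the 80% target. By comparison, Bonferroni over three pairs needs 22 per arm before inflation: 22 × 1.2 = 26.4, rounded up to 27; 27 × 1.1 = 29.7, rounded up to 30; so 90 in total.

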## Statistical Analysis of data

- Statistical analysis will be undertaken for the primary outcomes relating to the three types of bariatric surgery being utilised in current clinical practice using commercially available statistical programs in consultation with professional statistical advice from our Unit's established connection with a health research statistician.
  - Normally distributed data will be reported as mean  $\pm$  standard error of the mean and statistical comparisons between groups will be made using parametric statistical tests.
  - Data that is not normally distributed, will be analysed using non-parametric statistics with reporting of median (interquartile range) and comparisons by applying non-parametric statistical tests with post-hoc analysis for differences across the 3 surgical groups.
  - Proportionate data will be compared using tests such as a Fisher's exact test or  $X^2$  test.
- The results will be presented at a relevant scientific forum and subsequently be submitted for publication in a peer-reviewed medical journal.

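### The sample size allows for clustering by surgeon, but the tests named for comparing operations contain no surgeon term; how far this distorts P values depends on a surgeon-by-operation layout that the protocol does not give

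*Protocol*

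**What the plan says.** Protocol section 4.4 bases the sample size on a "Fisher's Exact Conditional Test for Two Proportions" with 80% power, alpha 0.05 and reflux rates given as "5% vs 50%, which represents a 'best estimate' of bile reflux post-operatively due to lacking published data". It then treats clustering as a fact: "Because there is clustering on surgeon in this data, an inflation factor (IF) was used to account for correlation within surgeon". The size of the allowance is given as "So IF for 5 surgeons and ICC=0.05 is 1.2". For dropout, "An additional 10% was then added to account for loss to follow-up". The result is 24 per operation and 72 in total.

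Section 4.5.3 leaves the type of operation to the treating surgeon together with the patient. Section 7.1 confirms that there is no randomisation.

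Section 9, under the heading on statistical analysis, covers three kinds of data. For normally distributed data, "statistical comparisons between groups will be made using parametric statistical tests". Other continuous data get non-parametric tests with post-hoc comparisons of the three operations. For proportions, "Proportionate data will be compared using tests such as a Fisher's exact test", with chi-square as the alternative. Surgeon, stratification, random effects and cluster-robust errors are not mentioned. The section also refers to professional statistical advice.

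**The concern.** The two sections rest on different assumptions. Section 4.4 says that patients of the same surgeon resemble each other. The Fisher and chi-square tests named in section 9 assume that all patients are independent. A larger sample recovers the power that clustering costs, provided that the analysis allows for clustering. It does nothing for the standard error of an analysis that does not.

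There are two consequences. If surgeons concentrate on particular operations, one surgeon with unusually high or low reflux can look like an operation effect, and the test rejects too often. If surgeons spread evenly over operations, the unadjusted tests are slightly conservative. Section 3.5 says the study is meant to inform the choice of operation, so a surgeon effect reported as an operation effect would mislead on the main question.

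**Working it through.** **1. The plan's own figure.** Exact power of the two-sided Fisher test (sidedness is not stated; two-sided assumed) for 5% against 50% at alpha 0.05 is 77.7% with 16 per arm and 81.3% with 17. The base size is therefore 17.

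- Inflation factor: 1 + (5 − 1) × 0.05 = 1.2
- 17 × 1.2 = 20.4, rounded up to 21
- 21 × 1.1 = 23.1, rounded up to 24
- 24 × 3 = 72

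The stated size reproduces, and the clustering allowance is part of it. Whether 1.2 is the right factor is a separate question.

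**2. The plan's factor taken at its word.** If the variance is 1.2 times what independence implies, a normal test that ignores this has an effective critical value of 1.96/√1.2 = 1.79. Its two-sided error is then about 7.4% instead of 5%.

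**3. Why the layout decides the size.** Let w_aj be the share of operation a's 24 patients treated by surgeon j, and ρ the ICC. For the difference between operations a and b, the true variance divided by the variance under independence is

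(1 − ρ) + 12ρ × Σ_j (w_aj − w_bj)².

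The protocol gives no surgeon-by-operation counts, so the layouts below are assumptions (five surgeons, 24 patients per operation):

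- *Even*: each surgeon does 4 or 5 of every operation.
- *Partial overlap*: (10, 8, 2, 2, 2), (2, 2, 10, 8, 2) and (3, 3, 3, 3, 12) for the three operations.
- *Specialised*: (14, 10, 0, 0, 0), (0, 4, 14, 6, 0) and (0, 0, 0, 8, 16).
- *Nested*: (12, 12, 0, 0, 0), (0, 0, 12, 12, 0) and (0, 0, 0, 0, 24).

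With ρ = 0.05, for the first against the third operation:

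- Even: the sum is close to 0, so the ratio is about 0.95.
- Partial: (7² + 5² + 1² + 1² + 10²)/24² = 176/576 = 0.306; 0.95 + 0.6 × 0.306 = 1.13.
- Specialised: (14² + 10² + 8² + 16²)/24² = 616/576 = 1.069; 0.95 + 0.6 × 1.069 = 1.59.
- Nested: 0.25 + 0.25 + 1 = 1.5; 0.95 + 0.6 × 1.5 = 1.85.

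**4. Simulated type I error.** No operation effect; common reflux rate 27.5% (assumed midpoint of 5% and 50%); ICC 0.05; beta-binomial outcome for the proportions and a normal outcome for ANOVA; at least 20,000 runs per setting; nominal level 5%.

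| Layout | 3-group chi-square | Pairwise Fisher | ANOVA |
|---|---|---|---|
| Independent patients (ICC 0) | about 5% | about 2.5% | about 5% |
| Even | 4.1% | 2.4% | 4.4% |
| Partial overlap | 7.4% | 3.8% | 7.4% |
| Specialised | 13.4% | 6.4–8.1% by pair | not run |
| Nested | 18.2% | 10.3% | 18.7% |

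Other partial-overlap layouts gave 5.3–6.4% for chi-square and 2.5–3.9% for Fisher. With a common rate of 50%, the nested figures are 18.6% and 11.4%. If the ICC were 0.10, the nested figures at 27.5% would be 32.3% and 19.2%; the protocol does not use that ICC.

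**5. What stratifying does.** A Mantel-Haenszel test stratified by surgeon stays at or below 5% in the three layouts where it can be run. In the nested layout no surgeon does two operations, so it cannot be run. Its power, compared with the unstratified test, is about 93% against 93% (even) and 86% against 92% (partial). In the specialised layout it falls to about 21%. There, no surgeon does both the first and third operations. The first against the second rests on one surgeon (10 and 4 patients), and the second against the third on another (6 and 8).

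**The case against.** A reader might infer that the protocol commits itself to independence tests only. It does not. The wording for proportions is illustrative, parametric tests could include a model with a surgeon term, statistical advice is foreseen, and an SAP that is not shown may settle the matter. This stands as a limit on the claim. It does not remove the mismatch: both tests named for proportions assume independence, the sample size was computed with one of them, and nothing tells the analyst to carry the stated clustering forward.

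A reader might also infer that P values are wrong whenever surgeon and operation overlap. The figures do not support that. At ICC 0.05 Fisher, the test behind the sample size, stays below 5% under partial overlap, and chi-square rises only to 6–7%. The large errors need near-nesting. The documents do not show near-nesting: patients share in the choice of operation, and section 7.1 says that individual patient factors weigh heavily in what is offered. Nor do they rule it out.

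Two further objections stand in part. The remedy is weakest where the problem is worst, because five specialised surgeons leave little within-surgeon information. And confounding by surgeon belongs to any non-randomised cohort, a design the protocol openly chooses; that is a reason to show the overlap, not to leave surgeon out of the analysis.

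**Conclusion.** The mismatch is in the text and is clear: clustering by surgeon is asserted and paid for in section 4.4, then dropped from the tests named in section 9. The harm is conditional. At the protocol's ICC of 0.05, the three-group chi-square test has a true type I error of about 4% with evenly spread surgeons, 6–7% with partial overlap and 13–18% with mostly or wholly specialised surgeons. Pairwise Fisher has about 2%, 3–4% and 6–11%.

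These figures rest on assumed layouts, a common reflux rate of 27.5% (the 11% comes from a 50% rate) and five surgeons. The direction does not depend on the exact rate, but the size depends heavily on the layout. The point should be corrected before analysis. It does not show that the study's result will be wrong.

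**What to change.** In section 9:

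- Make the main comparison of reflux proportions a test stratified by surgeon (exact or Mantel-Haenszel).
- Include surgeon as a term in the models for continuous outcomes.
- Record the operating surgeon for every participant and report the surgeon-by-operation table. The protocol text does not list surgeon as a study variable, although it should be easy to obtain.
- State in advance that, if surgeon and operation prove nearly nested, the unadjusted comparison will be reported as descriptive, with a statement that the operation effect cannot be separated from the surgeon.

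This changes analysis wording and adds one data item; it needs no extra patients or procedures. The statistical cost is little or no power if surgeons overlap across operations, and a large loss (to about 21% in the specialised layout) if they do not. That loss reflects what such data can support.

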#### 4.5.3. SURGERY

- Determination of the type of operation (LSAGB vs LSG vs LRYGB) to be performed will be at the discretion of the treating surgeon and informed patient preference.
- The operations will be performed by consultant oesophagogastric surgeons at the Royal Adelaide Hospital, The Queen Elizabeth Hospital, Western Hospital, Burnside War Memorial Hospital, Calvary Wakefield Hospital, Flinders Private Hospital or Ashford Hospital.

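### The clustering inflation factor is computed from the number of surgeons instead of patients per surgeon, so the 80% power claimed for 72 patients is not derived from the plan's own formula

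*Protocol*

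**What the plan says.** Protocol section 4.4 gives the sample size as follows: "A sample size of 72 (24 in each of the 3 study arms) is required". The basis is a "Fisher's Exact Conditional Test for Two Proportions" with 80% power, α = 0.05, and bile reflux rates of 5% and 50% in the best and worst operation.

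The section then adjusts for surgeon: "Because there is clustering on surgeon in this data, an inflation factor (IF) was used to account for correlation within surgeon". The formula is 1 + (m − 1)p, with m defined as the cluster size and p as the intra-class correlation coefficient (ICC). It is evaluated in one sentence: "So IF for 5 surgeons and ICC=0.05 is 1.2". A further 10% is added for loss to follow-up, and the number per group is multiplied by 3.

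On who performs which operation, section 4.5.3 says only that the choice "will be at the discretion of the treating surgeon and informed patient preference". No section gives the expected number of patients per surgeon, or says whether a surgeon performs one operation or several.

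**The concern.** The cluster is the surgeon, so m has to be a number of patients per surgeon. The figure put in is the number of surgeons. These are different quantities, and the design effect depends on the first.

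This is the study's only sample size justification. If the factor is too small for the caseloads that arise, 72 patients give less than 80% power for the protocol's own target contrast. A non-significant comparison could then be taken as reassurance about bile reflux after one of the operations, on the strength of a power figure that was never established. Section 3.5 says that the results are meant to inform surgical decisions about the safety of the single anastomosis bypass, so that misreading would matter.

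**Working it through.** **Inputs, all from Protocol section 4.4:** 5% vs 50%; Fisher's exact test; α = 0.05; 80% power; 5 surgeons; ICC 0.05; 10% loss; 24 per arm; 3 arms. Sidedness is not stated. Two-sided is assumed because it reproduces the stated figure, whereas a one-sided test would need only 14 per arm before inflation, or 57 in total.

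**1. Reproducing the 72.** Exact power of the two-sided Fisher test, by full enumeration:

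| n per arm | Power, 5% vs 50% |
|---|---|
| 12 | 58.8% |
| 13 | 65.6% |
| 14 | 71.2% |
| 16 | 77.7% |
| 17 | 81.3% |
| 18 | 84.4% |

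- The unadjusted requirement is 17 per arm by exact calculation.
- From 18 per arm: 18 × 1.2 × 1.1 = 23.76, rounded up to 24; 24 × 3 = 72.
- From 17, rounding up at each step: 17 × 1.2 = 20.4 → 21; 21 × 1.1 = 23.1 → 24; again 72.

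**2. What was entered as m.** 1 + (5 − 1) × 0.05 = 1.20. The stated factor is therefore the formula evaluated at m = 5, the number of surgeons.

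**3. What m would be under two possible splits.**

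*Even spread: each surgeon does an equal share of every operation.*
- Patients per surgeon within an arm: 24/5 = 4.8.
- Factor: 1 + 3.8 × 0.05 = 1.19.
- Evaluable per arm after 10% loss: 24 × 0.9 = 21.6.
- Effective n: 21.6/1.19 = 18.2 per arm; power about 84% (n = 18).
- A surgeon effect common to all operations also partly cancels from the comparison here, so even 1.19 is likely to be cautious.

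*Surgeons nested in operations: each does mainly one.*
- Patients per surgeon: 72/5 = 14.4 on average.
- Factor: 1 + 13.4 × 0.05 = 1.67.
- Effective n: 21.6/1.67 = 12.9 per arm; power 58.8% (n = 12) to 65.6% (n = 13).
- Counting only evaluable patients in m: 14.4 × 0.9 = 12.96; factor 1.60; effective n 13.5; power 65.6% (n = 13) to 71.2% (n = 14).
- At an effective 13 per arm, power reaches 80% at about 5% vs 58% (80.8%).

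**4. What the protocol's steps would give in the nested case.** From 17: 17 × 1.67 × 1.1 = 31.2 → 32 per arm, 96 in total. From 18: 18 × 1.67 × 1.1 = 33.1 → 34 per arm, 102 in total. With the number of surgeons fixed at 5, m grows with the total. Solving for both together from a base of 17 gives about 111–126. These totals show the size of the effect and are not a recommendation.

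**5. Sensitivity to the ICC, nested case, m = 14.4.**
- ICC 0.02: factor 1 + 13.4 × 0.02 = 1.268; effective n 17.0; power about 81%.
- ICC 0.10: factor 1 + 13.4 × 0.10 = 2.34; effective n 9.2; power about 39%.

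**The case against.** Three arguments can be made for leaving the figure alone.

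**The factor is applied per group, where m is about 5 anyway.** Section 4.4 inflates the number per group and only then multiplies by 3. Within an arm, 24/5 = 4.8 patients per surgeon, so 1.2 is almost exactly right under an even spread. The figure of 14.4 pools all three arms and suits only surgeons who do mainly one operation. This stands as far as it goes, and it is why a reader who infers that 72 patients definitely fail to reach 80% power goes too far. Section 7.1 describes the choice of operation as driven largely by individual patient factors, which gives no support to full nesting. Nor does it establish an even spread, and section 4.5.3 leaves the choice to surgeon and patient. Section 4.4 does not argue from 4.8 per arm either; it names the number of surgeons. The agreement between 4.8 and 5 is a coincidence of the final sample size.

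**The named test would have more power than 59–66%.** Simulating an unadjusted Fisher test with surgeons nested in operations, ICC 0.05 and 21–22 evaluable per arm, gives rejection in about 87–89% of runs at 5% vs 50% with two surgeons per arm. The simulation is sound, but that test ignores the clustering that section 4.4 says it allows for. Its type I error is about 6–7% with two surgeons per arm and about 10–12% with one, depending on the model. The excess is small in the milder case, but the simulation does not supply the cluster-adjusted 80% that the protocol claims.

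**Both the ICC and the 5% vs 50% are guesses.** This is true, and section 4.4 says that published data on reflux rates are lacking. It is a reason to show a range and does not validate a mis-entered input.

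**Conclusion.** The substitution is plain on the face of section 4.4: m is defined as cluster size and the number of clusters is used. The factor of 1.2 and the 80% power attached to 72 patients are therefore not derived from the protocol's own formula.

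The consequence is conditional. With 5 surgeons, ICC 0.05 and 10% loss, the factor runs from about 1.19 to about 1.67 and power for 5% vs 50% from about 84% to about 59–66%, according to a surgeon-by-operation split that the protocol does not state. A reader might conclude that the study is underpowered. The document does not support that, because under an even spread 72 is enough. It equally does not support a flat 80%.

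The power figures rest on a two-sided test, equal caseloads, and the effective-sample-size approximation, in which the evaluable number is divided by the factor and Fisher's test applied to the result.

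**What to change.** In section 4.4, keep the sample size at 72 and make these changes:

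1. Set m to the expected number of patients per surgeon, and delete the evaluation based on the number of surgeons.
2. State the expected surgeon-by-operation split, for example as a small table from the surgeons' recent caseloads.
3. Replace the flat 80% with the resulting power. If the split cannot be forecast, give the range (about 60% to 84% for 5% vs 50%, ICC 0.05, 10% loss), or state the contrast detectable with 80% power in the unfavourable case, 5% vs about 58%.
4. If surgeons are expected to perform several operations, stratify the comparison by surgeon, so that the analysis uses the cancellation of shared surgeon effects.

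The cost is a revised paragraph and a less favourable stated power. No extra patients are needed.
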